### 9.5.2.1.4.1 MedAvante Reporting of Safety/Adverse Events

MedAvante Raters will complete a safety reporting form (ie, Potential Clinical Events Notification Form), including an additional risk assessment form if certain triggers are met during their interviews with the patients at the study centers (ie, risk assessment forms for suicide, homicide, suspected child abuse, and suspected elder/dependent adult abuse). MedAvante Raters feel morally and ethically obligated to report this information to the study center, and the principal Investigator is responsible for follow-up, including management of the patient and further reporting as necessary.

Patients may spontaneously report possible clinical events to the centralized rater during an assessment. Possible clinical events as determined by the centralized rater will be recorded on a central rater source document and will be forwarded to the study center for further evaluation at the conclusion of the assessment. It is the study center's responsibility to determine, with further patient questioning, whether this event qualifies as an AE or SAE and to adhere to the methods described in Section 9.5.2.1.3 for reporting such events to the Sponsor.

If, while conducting the assessment, the centralized rater feels that there is an emergent risk to the safety of the patient, or to a third party, the study center will be contacted immediately by the centralized rater to intervene in the patient assessment room. The central rater shall stay on the teleconference call with the patient until appropriate personnel from the study center arrive. Information regarding the assessment shall be documented by the central rater and forwarded to the study center where the patient is physically present. The principal Investigator at the study center shall be responsible for compliance with any state law reporting requirements such as, for example, those governing the reporting of child abuse, or any duty to warn third parties of potential harmful conduct by the patient.

# 9.5.2.2 Immediate Reporting of Serious Adverse Events and Events of Special Interest

The Sponsor is required to inform worldwide regulatory authorities of SAEs that meet specific criteria. Therefore, the Sponsor must be notified immediately regarding any SAE that occurs after informed consent is obtained.

Within 24 hours of learning of any AE that meets one of the criteria for an SAE, the study center personnel must report the event to Global Drug Safety on the SAE Form for Clinical Trials. The Study Physician may also be notified by telephone.

If, during follow-up, any nonserious AE worsens and eventually meets the criteria for an SAE, that AE should be recorded as a new SAE.

The study center must transmit the SAE Form for Clinical Trials to the SAE fax number shown below. Even if an initial report is made by telephone, the SAE Form for Clinical Trials completed with all available details must still be faxed within 24 hours of knowledge of the event at the study center.

Supplemental information should be submitted as soon as available and may include laboratory results, radiology reports, progress notes, hospital admission and emergency room notes, holding and observation notes, discharge summaries, autopsy reports, and death certificates.

The Investigator is expected to take all therapeutic measures necessary for resolution of the SAE. Any medications or procedures necessary for treatment of the SAE must be recorded on the appropriate pages of the patient's eCRF. All SAEs are to be followed by the study staff until resolution or until the SAE is deemed stable. The Sponsor may contact the study center to solicit additional information or follow up on the event.

## 9.5.2.3 Reporting of Pregnancies Occurring During the Study

Study center personnel must report every pregnancy from the time the patient signs the ICF until 30 days after the last dose of IP. Within 24 hours of learning of the pregnancy, the study center personnel must report the event to Global Drug Safety on the Clinical Trial Pregnancy Form and fax it to the SAE/Pregnancy fax number provided in Section 9.5.2.2, even if no AE has occurred. Pregnancies in female partners of male patients occurring during the time frame described above must also be reported.

Any pregnancy of a patient treated with IP (or in female partners of male patients occurring during the time frame described above) must be followed to term and the outcome reported by completing a follow-up Clinical Trial Pregnancy Form. If the pregnancy is associated with an SAE (eg, if the mother is hospitalized for hemorrhage), a separate SAE Form for Clinical Trials must be filed as described in Section 9.5.2.2 with the appropriate serious criterion (eg, hospitalization) indicated in addition to the pregnancy form.

[figure not shown]

[figure not shown]
#### 9.5.6 Schedule of Assessments

[figure not shown]
The schedule of study procedures and assessments is tabulated by visit in the Schedule of Evaluations in Section 2.0. The descriptions of the procedures to be performed at each visit are provided in the following sections.

[figure not shown]
Upon providing written informed consent, patients enter a screening period of up to 14 days. Following the screening period, patients enter the 3-week, double-blind treatment period. During the double-blind treatment period, patients have 3 study visits per week. The visits occur in the following pattern: treatment day, 1 day following the treatment day, 4 days following the treatment day, and 7 days following the treatment day (which is the next treatment day). If necessary, study visits may be conducted up to 2 days before or after the scheduled visits with the exception of visits which are 24 hours apart (ie, Visits 2 and 3 must be conducted 1 day apart; similarly, Visits 5 and 6 as well as Visits 8 and 9 must be conducted 1 day apart). Upon completion of the double-blind treatment period, patients are eligible to enter the RAP-MD-04 maintenance study or enter a 1-week safety follow-up period.

[figure not shown]

[figure not shown]

[figure not shown]

#### 9.5.6.13 Unscheduled Visits

Unscheduled visits can be performed if safety concerns arise and at the discretion of the Investigator. Additional examinations may be performed as necessary to ensure the safety and well-being of the patients during the study.

### 9.6 DATA QUALITY ASSURANCE

# 9.6.1 Data Monitoring

Before any patient enters the study, a representative of the Sponsor will meet with the Investigator and the study center staff to review the procedures to be followed during the study. Electronic data capture (EDC) functionality training is provided via computer-based training to train investigators and authorized designees on recording the data in the eCRFs using the EDC system. After the first patient is enrolled, the Sponsor representative, a Regional Site Manager or designee, will periodically monitor the progress of the study by conducting on-site visits. This Regional Site Manager or designee will review query statuses remotely, possibly warranting more frequent communication and/or study center visits with the Investigator and the study center staff. The Investigator will make available to the Regional Site Manager or designee source documents (written notes and electronic medical records, if used), signed consent forms, and all other study-related documents. The Investigator and the study center staff will be responsible for data entry of patient data into the eCRFs via the EDC system, resolving data queries generated via the EDC system and providing missing or corrected data. The Investigator or designee will be responsible for approving all changes performed on the data, and endorsing the patient data within the EDC system. This approval method will include applying an electronic signature linked to a uniquely assigned username and password that together will represent a traditional handwritten signature used in the past.

# 9.6.2 Data Recording and Documentation

Data collection will involve the use of the EDC system, to which only authorized personnel will have access. Patient's data are to be entered into the EDC system by the Investigator or designee using their assigned EDC user account. After data entry into the EDC system by the Investigator or designee, a combination of manual and programmatic edit checks will be used to review the data for completeness, logic, and adherence to study protocol. As a result of these edit checks, data monitoring, and reviews, queries may be electronically issued to the study center and should be answered electronically via the EDC system.

Each query will carry identifying information (assigned username, date, and time) to assist the Sponsor and the Investigator on the origin of the data clarification request and the response provided by the Investigator. All data changes made to the patient's data via a data query will be approved by the Investigator prior to final database lock.

After all data have been reviewed and all issues have been resolved, the database will be locked.

All data collected in the context of this study will be stored and evaluated per regulatory requirements and applicable guidance for electronic records. Also, data will be stored and evaluated in such a way as to guarantee patient confidentiality in accordance with the legal stipulations applying to confidentiality of data. Study records (eg, copies of eCRFs, laboratory reports, regulatory documents) will be retained at the study center, along with adequate source documentation, according to FDA and ICH requirements. All study records must be available for inspection by the Sponsor, its authorized representatives, the FDA, or other health authorities.

Source documents will be used at the study centers and may include a patient's medical record, hospital charts, clinic charts, the Investigator's patient study files, as well as the results of diagnostic tests such as laboratory tests, ECGs, etc. A centralized clinical laboratory will be used for the analysis of all blood samples. Additional information on the collection and handling of samples is detailed in the Lab Procedure Manual.

# 9.7 STATISTICAL METHODS AND DETERMINATION OF SAMPLE SIZE

# 9.7.1 Analysis Populations

*Three* populations will be considered in the statistical analysis of the study, as specified in the following subsections.

## 9.7.1.1 *Enrolled* Population

The *Enrolled* Population will consist of all patients who sign informed consent, receive a patient identification (PID) number, *and enter into screening*.

## 9.7.1.2 Safety Population

The Safety Population will consist of all patients who *receive* at least 1 dose of randomized IP.

#### 9.7.1.3 *Modified* Intent-to-Treat Population

The *modified* Intent-to-Treat (*m*ITT) Population will consist of all patients *who are* randomized, receive at least 1 dose of IP and have at least 1 postbaseline assessment of the MADRS total score.

### 9.7.2 Patient Disposition

The number and percentage of patients in the *Enrolled*, Safety, and *m*ITT populations will be summarized by treatment group and study center.

Screen-failure *patients* (ie, patients screened but not *included in the Enrolled Population*) and the associated reasons for failure to randomize will be tabulated overall for *all screened patients*.

The number and percentage of patients *in the mITT Population* who complete the double-blind treatment period *and of* patients who prematurely discontinue during the same period *will be presented for each treatment group and pooled across treatment groups*. The reasons for premature discontinuation *during* the double-blind treatment period as recorded on the *disposition* pages of the eCRFs will be summarized by treatment group for the *mITT* Population.

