#### 5.3 PATIENT INFORMATION AND INFORMED CONSENT

After being given an explanation of the study and before participating in any study procedures, each patient must provide written informed consent in compliance with 21 CFR, Parts 50 and 312 and give HIPAA authorization.

Each patient will read and sign an ICF and/or other authorization form as per local regulations; each patient will be made aware that he or she may withdraw from the study at any time.

The ICF contains all the elements of informed consent listed in Appendix I of this protocol. Signed copies of the ICF and the HIPAA or other locally applicable form will be given to the patient, and both documents will be placed in the Investigator's study files.

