# 9.1.1 Screening Period

After providing written consent, patients will enter a screening period of up to 14 days. The screening/washout period will be up to 2 weeks prior to Visit 2. Screening procedures may be conducted on up to 2 separate dates where necessary to accommodate patient and study center schedule; however, every effort should be made to conduct all procedures as early as possible in the screening period and the rater-administered MADRS and computer-administered MADRS must be collected on the same date. Patients will not receive any investigational product (IP) during the screening period but must continue their background ADT at the same dose. Patients meeting the eligibility criteria at the end of Visit 2 (Baseline) will be assigned a treatment by the interactive web response system (IWRS) and enter the double-blind treatment period.

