# 9.3.3 Removal of Patients from Therapy or Assessment

A premature discontinuation will occur when a patient who signed the ICF ceases participation in the study, regardless of circumstances, before the completion of the study visits and procedures. Patients can be prematurely discontinued from the study after careful consideration for one of the following reasons:

- Screen failure (failure to meet inclusion/exclusion criteria or pregnancy)
- Pregnancy
- Withdrawal of consent
- AE
- Any patient may be withdrawn due to AE at the discretion of the Investigator
- Any patient who meets any of the following criteria at any point during the study must be withdrawn from participation, due to AEs related to suicide:

In the event that a patient is withdrawn for a suicide-related AE, the patient should be referred for additional treatment or hospitalization, as clinically indicated, in addition to withdrawing the patient from the study.

- Lack of efficacy
- Protocol violation
- Noncompliance with IP
- Noncompliance with ADT

- Lost to follow-up
- Study terminated by Sponsor
- Study center terminated by Sponsor
- Other

All randomized patients who prematurely discontinue from the study, regardless of cause, should be seen for a final assessment at an Early Termination (ET) Visit. A *final assessment* will be defined as completion of the evaluations scheduled for all patients at Visit 11. All patients discontinuing the study prematurely should enter the 1-week safety follow-up period.

Patients who discontinue from the study and do not return to the study center for final assessments must be requested in writing to return to the study center for a final assessment. A copy of the letter, together with the source documentation, will be kept in the Investigator's files. The reason for premature discontinuation from the study will be recorded on the Study Termination Page of the eCRF. Study center staff will be contacted by the Sponsor after each premature discontinuation to ensure proper characterization of the reason for discontinuation is captured.

[figure not shown]

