### 9.4.5 Method of Assigning Patients to Treatment Groups

After a patient signs the ICF at Screening (Visit 1), study personnel will register the patient in the IWRS, and the system will assign the patient a sequential PID.

The IP will be labeled with medication kit numbers. The IWRS will provide the study center with the specific medication kit number(s) for each randomized patient at the time of randomization. Study centers will dispense IP according to the IWRS instructions. Study centers will also log onto the IWRS at subsequent visits to obtain a study medication kit number for dispensing IP. Study centers will receive the IWRS confirmation notifications for each transaction. All notifications are to be maintained with the study source documents.

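### Section 9.7.2 defines screen failures in a way that is empty under Section 9.7.1.1, and its mITT-only discontinuation table omits randomized patients who leave before a dose or a first postbaseline MADRS

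*Protocol*

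**What the plan says.** Protocol Section 9.7.1 names three analysis populations: Enrolled, Safety and mITT. None is defined as all randomized patients.

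- **Enrolled (9.7.1.1):** the "Population will consist of all patients who sign informed consent, receive a patient identification (PID) number" and enter screening. Randomization is not a condition.
- **mITT (9.7.1.3):** randomized, at least one dose, and at least one postbaseline MADRS total score.

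Section 9.7.2 then sets out three things:

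- Population counts: "The number and percentage of patients in the *Enrolled*, Safety, and *m*ITT populations will be summarized by treatment group and study center".
- A screen-failure table, with the reasons patients were not randomized. Its subjects are described as "ie, patients screened but not *included in the Enrolled Population".
- Completion, premature discontinuation and reasons for the double-blind period, all restricted to the mITT.

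Four other sections bear on this:

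- Section 5.3: "After being given an explanation of the study and before participating in any study procedures, each patient must provide written informed consent".
- Section 9.4.5, once the consent form is signed at Visit 1: "study personnel will register the patient in the IWRS, and the system will assign the patient a sequential PID".
- Section 9.1.1: consented patients enter screening, and those eligible at the end of Visit 2 "will be assigned a treatment by the interactive web response system (IWRS) and enter the double-blind treatment period".
- Section 9.3.3: "A premature discontinuation will occur when a patient who signed the ICF ceases participation in the study, regardless of circumstances", if this happens before the study visits and procedures are complete. The first reason listed is "Screen failure (failure to meet inclusion/exclusion criteria or pregnancy").

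**The concern.** There are two separate faults in one section.

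The first is a contradiction between definitions. If everyone screened is Enrolled, nobody can be screened and not Enrolled. The screen-failure table then has no subjects, although the same sentence asks why they were not randomized. Never-randomized Enrolled patients also have no treatment group, so a by-arm summary of the Enrolled Population cannot cover that population.

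The second is the choice of table population. Membership of the mITT depends on having been dosed and having been rated afterwards. A discontinuation table restricted to it removes the earliest losses, which are among those a disposition table is meant to explain. The study is intended to support a regulatory application (Section 7.0), so patient accounting should run without a gap from consent to completion.

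**Working it through.** **Part 1: the definitions side by side**

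Let S be the screened patients and E the Enrolled Population.

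1. A patient in S has consented, because consent precedes any study procedure (5.3).
2. That patient has a PID, assigned after the consent form is signed at Visit 1 (9.4.5).
3. That patient has entered screening (9.1.1).
4. These are the three conditions for E (9.7.1.1), so S lies within E and S minus E is empty.

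The literal count of screen failures is 0, whatever the true number. Section 9.3.3 disagrees: it treats screen failure as something that happens to patients who have signed the consent form, that is, inside E. The set evidently meant is Enrolled patients who were not randomized.

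**Part 2: who is missing from the discontinuation table**

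Randomized minus mITT consists of (a) patients randomized and never dosed and (b) patients dosed with no postbaseline MADRS. Both groups are in the double-blind period from treatment assignment (9.1.1). If they stop, both are premature discontinuations (9.3.3). Neither can appear in a table restricted to the mITT.

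Much of the count can be recovered from other planned summaries:

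- If the by-arm Enrolled counts are in practice the randomized patients, Enrolled minus Safety gives group (a) and Safety minus mITT gives group (b).
- Section 9.7.4.1 tabulates the number of doses received by arm.
- Section 9.7.6.1 summarizes adverse events leading to discontinuation in dosed patients.

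The other reasons for these patients are not tabulated in the visible protocol text.

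**Size, for illustration only**

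Let N be the number randomized, d the number who discontinue, and k the number of those outside the mITT. The protocol gives none of the final d, the per-arm d, or k; all are assumed here.

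- True rate: d/N
- Rate in the table: (d − k)/(N − k)
- Understatement: k(N − d)/[N(N − k)]

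| Case | True rate | k = 1 | k = 2 | k = 3 |
|---|---|---|---|---|
| All arms, N = 630, d = 31 | 31/630 = 4.92% | 30/629 = 4.77% | 29/628 = 4.62% | 28/627 = 4.47% |
| One arm, N = 210, d = 10 | 10/210 = 4.76% | 9/209 = 4.31% | 8/208 = 3.85% | not run |

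For k = 1 the understatement is 599/(630 × 629) = 0.151 points overall and 200/(210 × 209) = 0.456 points in one arm. With k = 0 there is none.

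The overall result depends little on the assumed rate. At the 15% dropout used for planning in Section 9.7.9 (0.15 × 630 = 94.5; take d = 94), k = 1 gives 536/(630 × 629) = 0.135 points.

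**The case against.** **The first part corrects itself.** The sentence asks for reasons for not being randomized, across all screened patients, so a programmer would be unlikely to produce an empty table. A reader might infer that the screen-failure data will be lost; the text does not support that. This stands, and it makes the first part close to clerical.

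**The fault may lie in 9.7.1.1 instead.** Sections 9.1.2 and 9.7.9 use enrolment to mean randomization. If Enrolled was meant that way, Section 9.7.2 is coherent on both screen failures and by-arm counts, and it is the Enrolled definition that is misworded. This also stands. The two sections conflict, and either could be corrected.

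**Using the mITT for disposition is an explicit choice that no other section forbids.** That is true. Omissions should also be rare:

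- The first dose falls on the day of assignment (9.4.7.2).
- Visit 3 is one day later, and dosed patients are required to complete Visit 11 (9.1.2).
- An early termination visit is expected, and the reason for leaving is recorded in the eCRF for every premature discontinuation (9.3.3).

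These features limit the size of the problem but do not remove it. When an early loss does occur, the stated rule drops it from the table.

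**The missing reasons may be reported elsewhere.** Parts of the protocol text are not visible and the SAP is not at hand. The claim is therefore limited to the visible text; it cannot be said that these reasons are reported nowhere.

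**The interim dropout figure is not a ceiling.** A reader might take the dropout rate below 5% in Section 9.7.9 as capping discontinuations at 31 of 630. It does not. It was observed when somewhat more than 590 patients were enrolled and enrolment was still open, and its denominator population is not stated. The 31 used above is an assumption only.

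**Conclusion.** Both parts hold, and both are minor.

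The contradiction between Sections 9.7.1.1 and 9.7.2 follows from the text alone and needs no assumption. Its practical effect is small: the intended table can be built, but only by departing from one of the two stated definitions.

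The mITT-only rule understates discontinuation whenever a randomized patient leaves before a dose or before a first postbaseline MADRS. The amount is about 0.15 points per such patient overall and about 0.46 points in one arm, at an assumed rate near 5%. The number of such patients is unknown, probably small and possibly zero.

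A reader might infer that attrition in this trial is materially understated or that the efficacy results are compromised. The documents support neither. They give no count of omitted patients, and the discontinuation table does not enter the primary or key secondary analysis. Efficacy estimates, power and type I error are unaffected.

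**What to change.** 1. Reconcile Sections 9.7.1.1 and 9.7.2 in one of two ways:
   - Keep the Enrolled definition, define screen failures as Enrolled patients who are not randomized, report Enrolled overall and by study center, and add a Randomized Population to be summarized by treatment group and center with Safety and mITT.
   - Or redefine Enrolled as all randomized patients and add a separate Screened Population for the screen-failure table.
2. Base completion, premature discontinuation and reasons on all randomized patients.

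The cost is wording and one table population. No new data are needed, because the reason for each premature discontinuation is already recorded in the eCRF. The only downside is that the reported discontinuation rate may be slightly higher.
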